## **Samples Concerns**

A urine specimen will be collected for cytology and pregnancy testing. The specimen will be discarded as per routine destruction methods.

The tissue collected from the bladder lesions will be processed and assessed for the immunohistochemistry and RT-qPCR tests in [name] laboratory at Main Baylor, Room 506C. Analysis will include normal H&E pathological examination and immunohistochemistry for Ki-67, TUNEL, ER $\alpha$  and ER $\beta$ -1, ER $\beta$ -2 and ER $\beta$ -5 will be performed, and RT-qPCR analyses will be performed for ER $\alpha$ , ER $\beta$ -1, ER $\beta$ -2 and ER $\beta$ -5.

Approximately two teaspoons of blood will be drawn for the analysis of CBC, platelets and bilirubin. Samples are destroyed as for any standard of care blood work. No cell lines will be developed with the specimen samples obtain during this study. No blood samples will be taken for any research study purpose.

The biopsy samples will be coded and labeled with a 3 digit number starting with 001, 002. This study number will only be linked to the clinical information by a log file, stored safely in the Department of Urology computer servers, protected behind BCM firewall and individual password protected system access. Only the PI and the authorized study staff will have access to this log file, being able to link the clinical information with the specimen numeric codes.

These specimen tissue samples will not be released to other hospitals or laboratories, and they will be used exclusively for regular clinical purposes and the research procedures described in this protocol.

[figure not shown]
These specimen tissue samples will not be banked for future use. If there is a remaining sample after the planned analyses are performed, these specimens will be kept until the completion of the study. These samples will not be available to other research projects for other testing.

If the study subject withdraws from the study or revokes authorization in writing, he/she will be removed from the study, but the remaining specimens will not be returned to the subject but will be destroyed upon written request sent to [name]. The data collected prior to destruction will not be deleted.

The study results will not be recorded in the subjects' medical records, because this information has no validated clinical meaning; therefore, no clinical use currently. For the same reason, the results from this study will not be revealed to the research study subject or his/her doctor who is not included in this study protocol. Subjects may never be able to obtain limited research health information.

**Sample Size:**

This is a single-arm, two-stage phase-II trial (Simon design) to demonstrate that treatment with 20 mg/day of oral tamoxifen for 12 weeks is associated with elimination or a greater than 30% reduction in size of a bladder cancer marker lesion from pre to post-treatment.

The table above shows the Simon’s two-stage phase-II study design plot, assuming that the bad response rate (P0) is 0.05, the good response rate (P1) is 0.30, significance level ( $\alpha$ ) is 0.05, power is 0.90, and confidence interval is 95%.

The optimal design was chosen to minimize the expected sample size, and reduce the number of subjects enrolled if the study is negative. According to this method, the maximum sample size is 17 and the minimum sample size is 9. The first stage of the study will include 9 patients. If there are 0 responses observed, the trial will be stopped accepting H0. If not, the trial continues to the stage-two, accruing 8 more patients (total of 17). If there are 2 or fewer total responses observed, or 3 or more total responses observed, then we will accept or reject H0, respectively.

Considering a 10% drop-off rate, the expected maximum sample size needed for this study will be 19 subjects, so we are able to accrue 17 evaluable subjects. Evaluable subjects meet all the eligibility criteria and receive at least 30 days of Tamoxifen. All subjects who take at least one dose of Tamoxifen will be evaluable for safety. Since the past five-year median accrual rate for this group of patients in our center has been 10-12 cases/year, we expect conservatively to complete accrual in 2 years.

**Data Analysis:** See below under End-points/Statistical considerations

**End-points/Statistical considerations:**

The primary outcome of interest is a composite endpoint, defined according to the RECIST (Response Evaluation Criteria in Solid Tumors) criteria. The response criteria evaluation of target lesions is defined as follows:

- *Complete Response (CR)*: Disappearance of all target lesions;

- *Partial Response (PR)*: At least a 30% decrease in the longest diameter of target lesions, taking as reference the baseline longest diameter;
- *Progressive Disease (PD)*: At least a 20% increase in the longest diameter of target lesions, taking as reference the baseline longest diameter recorded or the appearance of one or more new lesions;
- *Stable Disease (SD)*: Neither sufficient shrinkage to qualify for PR, nor sufficient increase to qualify for PD, taking as reference the baseline longest diameter.

The endpoint will be considered a positive response if the endoscopic outcome is a CR or PR, or the biopsy of a residual tumor or the bed of the lesion (in case of a CR) is negative for bladder cancer. If biopsy of the marker lesion at the end of the study is positive for bladder cancer, and according to RECIST criteria, the outcome is PD or SD, the treatment response to tamoxifen therapy will be considered negative. The table below displays the summary of endpoints.

	Cystoscopy	Biopsy	Final Overall Response
Positive response	CR	negative (bed)	CR → success
	PR/SD	negative	CR → success (no viable tumor with necrosis, fibrosis, or scar tissue)
	CR	positive (bed)	PR → success
	PR	positive	PR → success
	PD	negative (unlikely)	CR → success
Negative response	PD	positive	PD → failure
	SD	positive	SD → failure

**Notes:** CR=complete response; PR=partial response; SD=stable disease; PD=progressive disease.

[figure not shown]
Size will be measured in millimeters and analyzed as a composite dichotomous endpoint as defined above. For this trial, we will include patients with marker lesions ranging in size from 6 to 10 mm. As shown by data from our pilot study discussed earlier, we are able to measure these lesions accurately, with a standard deviation of 1.5mm, and we are able to statistically detect 15% reduction in size of these lesions.

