### **Specific Aims:**

**Aim 1.** Evaluate the efficacy of tamoxifen for treatment of low/intermediate-risk bladder tumors, assessing for the clinical response of the marker lesion, and analyzing the effects in tissue, in terms of affecting apoptosis and proliferation, while continuously monitoring for treatment toxicity.

**1a.** Evaluate the efficacy of tamoxifen for treatment of low/intermediate-risk bladder tumors, utilizing the RECIST criteria combined with the final biopsy of the marker lesion or the bed of the lesion in case of a complete response. (PRIMARY ENDPOINT)

**1b.** Evaluate the histopathologic effect of tamoxifen treatment in the tumor cells, assessing for the presence of necrosis, fibrosis, apoptosis and scar tissue.

**1c.** Evaluate the treatment effect in the histologic markers for apoptosis (TUNEL) and proliferation (Ki-67).

**1d.** Monitor treatment toxicity.

**Aim 2.** Evaluate the expression levels of ER $\alpha$  and ER $\beta$  (including splicing variants) before and after treatment with tamoxifen, in both normal and tumor tissues, and correlate the clinical response with the expression levels of these ERs.

**2a.** Report on and compare the pre and post-treatment expression levels of ER $\alpha$  and ER $\beta$  (including their splicing variants, more specifically ER $\beta$ -1, ER $\beta$ -2 and ER $\beta$ -5) in both normal and tumor tissues.

**2b.** Correlate the observed clinical effect, measured by the proportion of subjects that had complete or partial responses, with the pretreatment expression levels of ERs in tumor tissue.

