**Primary objective:**

Evaluate the efficacy of tamoxifen for treatment of low/intermediate-risk bladder tumors, assessing for the clinical response of the marker lesion.

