## **Design:**

### **Study design**

We will conduct a single-center, two-stage phase-II, clinical trial utilizing the marker lesion study design, where a tumor is mapped in the bladder, treated, and re-assessed after the study intervention to evaluate the effects of the therapy. This study design will allow the evaluation of the size of the tumor before and after treatment, and the histological assessment of treatment effect in normal and tumor tissues, as well as modulation of immunohistochemistry markers for apoptosis and proliferation, and of the expression levels of ER $\alpha$ , ER $\beta$ 1, ER $\beta$ 2, and ER $\beta$ 5.

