### **Overall study description**

Patients with primary or recurrent low/intermediate-risk papillary urothelial carcinoma of the bladder will undergo resection of all but one marker lesion, measuring at least 6mm but no greater than 10mm, and biopsy of normal-appearing mucosa. Patients with a solitary tumor will undergo only biopsy prior to treatment. A 2mm cold cup biopsy of the marker lesion will always be performed to rule out a potential high-grade lesion and for assessment of pretreatment immunohistochemistry expression levels of ER $\alpha$ , ER $\beta$ 1, Ki-67 (proliferation marker) and TUNEL (apoptosis marker). If there are multiple tumors, all lesions, except the marker lesion will be resected and sent for analysis. These patients will not receive single immediate post-operative intravesical instillation of mitomycin-C. They will then undergo a 12-week course of treatment with tamoxifen administered as a single daily oral dose of 20mg. At the completion of therapy, patients will undergo resection of the marker lesion (or biopsy of the tumor bed, if a complete response is observed) and biopsy of normal-appearing bladder mucosa again. Toxicity evaluations will be performed at the beginning (day 3), midway (week 6), and at completion of treatment (week 12), prior to resection of the marker lesion. A final assessment for toxicity will also be performed 30 days after completion of therapy as well as a second definitive resection of the marker lesion. Urine samples will be obtained with the index tumor in place (marker lesion), and after completion of treatment, at the time of definitive transurethral resection of the index tumor, as part of the standard clinical care of these patients, and at the discretion of the surgeon for assessment of urinary cytology. The urine samples will not be utilized for the research study. All normal-appearing bladder biopsies (pre and post-treatment), the additional tumors (in case of multiple lesions), and the definitive resection of the marker lesion (in the absence of response to therapy) will provide sufficient material for immunohistochemistry assessment of the expression levels of ER $\alpha$ , ER $\beta$ -1, ER $\beta$ -2, ER $\beta$ -5, Ki-67, and TUNEL, and also for RT-qPCR for mRNA analyses of ER $\alpha$ , ER $\beta$ -1, ER $\beta$ -2, and ER $\beta$ -5. The pretreatment biopsy of the marker lesion will be performed with a smaller biopsy forceps and will provide limited material, sufficient only for immunohistochemistry assessment of the expression levels of ER $\alpha$ , ER $\beta$ -1, Ki-67, and TUNEL.

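### The primary endpoint gives two scores, success and failure, to a marker responder with a positive marker biopsy and a new tumour, and states no precedence

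*Combined protocol and SAP*

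**What the plan says.** All references are to the combined protocol and SAP.

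**Response categories** (End-points/Statistical considerations). CR is disappearance of the target lesions. PR is a decrease of at least 30% in their longest diameter. Neither requires that new lesions be absent. PD is an increase of at least 20%, "taking as reference the baseline longest diameter recorded or the appearance of one or more new lesions".

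**Sentences above the table.** An endoscopic CR or PR counts as a positive response. So does a second route: "or the biopsy of a residual tumor or the bed of the lesion (in case of a CR) is negative for bladder cancer". The failure sentence begins "If biopsy of the marker lesion at the end of the study is positive for bladder cancer" and requires in addition that the RECIST outcome is PD or SD.

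**Table.** CR or PR with a positive biopsy is PR and success. PD with a positive biopsy is failure. PD with a biopsy marked "negative (unlikely)" is CR and success. The result column is headed as the final overall response.

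**What the biopsy samples.** Under Overall study description, at the end of treatment "patients will undergo resection of the marker lesion (or biopsy of the tumor bed, if a complete response is observed)". Aim 1a describes RECIST "combined with the final biopsy of the marker lesion or the bed of the lesion in case of a complete response". The tissue is the marker lesion or its bed. The table has no entry for tissue from a new tumour.

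**What the endpoint is about.** The Primary objective is efficacy, "assessing for the clinical response of the marker lesion". Study design describes a method "where a tumor is mapped in the bladder, treated, and re-assessed after the study intervention". Marker lesion study design, Sample Size and the text on Specific Aims 2a and 2b also tie response to the marker lesion.

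**The concern.** A new tumour makes a patient PD whatever the marker lesion has done, yet it does not stop the same patient from being CR or PR. When the table gives different results for the two categories, the primary endpoint has no defined value.

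The decision rule leaves little slack: stop at 0 of 9, and reject H0 at 3 or more of 17. One patient scored either way can turn a stop into continuation, or 2/17 (accept H0) into 3/17 (reject H0). The trial has a single arm and describes no blinded assessor, so an unstated precedence would be settled by someone who already knows the result. The same responder status enters the estrogen-receptor correlation of aim 2b.

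A second, lesser issue is the label. A patient with a new bladder tumour and a negative marker biopsy would be reported as a complete response in a column headed as the overall result, although that biopsy carries no information about a tumour elsewhere.

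**Working it through.** **1. The design reproduces.** Inputs from Sample Size: P0 = 0.05, P1 = 0.30, stop at 0/9, reject H0 at 3 or more of 17. With X1 ~ Bin(9, p) and X2 ~ Bin(8, p),

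P(reject) = P(X1=1)·P(X2≥2) + P(X1=2)·P(X2≥1) + P(X1≥3).

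- p = 0.05: 0.2985 × 0.0572 + 0.0629 × 0.3366 + 0.0084 = 0.0466.
- p = 0.30: 0.1556 × 0.7447 + 0.2668 × 0.9424 + 0.5372 = 0.9045.

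Both meet the stated 0.05 and 0.90.

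**2. Score each combination when a new tumour is present.** Each patient is looked up twice, once by the marker finding and once as PD.

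| Marker finding | Biopsy | By marker finding | As PD | Score |
|---|---|---|---|---|
| CR | negative | CR, success | CR, success | success |
| PR | negative | CR, success | CR, success | success |
| SD | negative | CR, success | CR, success | success |
| PD by size | negative | CR, success | CR, success | success |
| CR | positive | PR, success | PD, failure | **undefined** |
| PR | positive | PR, success | PD, failure | **undefined** |
| SD | positive | SD, failure | PD, failure | failure |
| PD by size | positive | PD, failure | PD, failure | failure |

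Two of the eight are undefined. The sentences above the table conflict for the same two: CR or PR is positive, while a positive biopsy with PD is negative. The four negative-biopsy rows have a fixed score, and only their label is at issue.

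**3. Size, for illustration.** The documents give no rate of new tumours alongside marker success, and no share of successes with a positive biopsy. Assumptions:

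- One-year recurrence r of 15% (low risk) and 24-38% (intermediate risk), from Defining disease stage, grade and risk-groups, converted at constant hazard: q = 1 − (1 − r)^(12/52), which gives 3.68%, 6.14% and 10.44%.
- New tumours are independent of marker response.
- A share s = 0.50 of successes is biopsy-positive.

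The rate of ambiguous patients is p·q·s. The shift is P(reject at p) − P(reject at p − p·q·s). The chance of at least one ambiguous patient in 17 is 1 − (1 − p·q·s)^17.

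| r | q | Shift at P0 (points) | Shift at P1 (points) | At least one in 17, P0 | At least one in 17, P1 |
|---|---|---|---|---|---|
| 15% | 3.68% | 0.21 | 0.78 | 1.6% | 9.0% |
| 24% | 6.14% | 0.35 | 1.34 | 2.6% | 14.5% |
| 38% | 10.44% | 0.58 | 2.37 | 4.3% | 23.5% |

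Example, r = 38% at P1: 0.30 × 0.1044 × 0.50 = 0.0157. P(reject) at 0.30 − 0.0157 = 0.2843 is 0.8809, and 0.9045 − 0.8809 = 0.0237.

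Other shares, over the same range of r: s = 0.25 gives 0.1-0.3 points at P0 and 0.4-1.1 at P1; s = 0.75 gives 0.3-0.9 and 1.2-3.7.

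**4. If every new tumour counted as failure.** This changes the endpoint, so it does not measure the ambiguity. The success rate becomes p(1 − q). From 0.30 it falls to 0.289, 0.282 and 0.269, with power 0.888, 0.876 and 0.853. With an assumed 12-week rate of 15% or 20%, it falls to 0.255 or 0.240, and power drops by 8.1 or 11.7 points to about 0.82 or 0.79.

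**The case against.** The best defence is context. The list of categories is introduced as an evaluation of target lesions, the failure sentence names the marker lesion, and the objective, design and sample-size text all point the same way. The PD row with a negative biopsy is marked unlikely, which suits an enlarged marker lesion without viable tumour. On this view the new-lesion clause is one stray phrase with an obvious intended reading. That stands as evidence of intent, and the fix follows it. It does not remove the conflict, because the clause is printed and an analyst could apply it.

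One could instead argue that citing RECIST implies that PD overrides. The plan writes out its own criteria and does not say so. That reading would also leave PD with a negative biopsy as CR and success.

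The smallness of the average effect is conceded.

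Three stronger readings are tempting and are not supported:

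- *That any new tumour makes the score ambiguous, or that the table prints two scores in one row.* Six of the eight combinations have a single score, and no row carries two. The double fit comes from overlapping definitions.
- *That the type I error is inflated.* The rule attains 0.0466 at P0. Scoring the ambiguous patients as failures only lowers the success rate, and the documents do not say that P0 was set on one reading or the other.
- *That the protocol's own definition makes a new tumour a recurrence.* That definition is background. It covers the same or lower stage or grade and calls a higher one progression, so without histology the class is unknown.

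**Conclusion.** The concern holds in a limited form, and the wording should be corrected. The primary-endpoint rule contradicts itself for a marker CR or PR with a positive marker biopsy and a new tumour. This can be read directly from the definitions and the table and needs no assumption. One such patient is enough to change the decision at 0/9 or 2/17.

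The average effect is modest: 0.2-0.6 percentage points in the probability of rejecting H0 at P0 and 0.8-2.4 at P1, under the constant-hazard, independence and 50% biopsy-positive assumptions. The P1 figures are too high if tamoxifen also suppresses new tumours in responders. They are too low if the 12-week new-tumour rate exceeds 10.4%, which the documents cannot exclude. The case for correction therefore rests on an undefined score, not on the size of the shift.

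The CR label on a patient with a new tumour and a negative marker biopsy is a separate reporting fault with no effect on the decision.

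**What to change.** Before outcome data are reviewed, score the primary endpoint on the marker lesion only:

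1. Delete the new-lesion half of "taking as reference the baseline longest diameter recorded or the appearance of one or more new lesions" from the PD definition used for the table. PD with a negative biopsy then means growth without viable tumour.
2. Head the result column as marker-lesion response.
3. Tabulate new bladder tumours seen at the end-of-treatment cystoscopy as a separate descriptive outcome, by marker response.

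The first step alone removes the ambiguity; the other two deal with the label. The cost is one clause, one heading, one small table and a record of whether new tumours were seen. P0, P1, the 0/9 and 2/17 rule and the power of 0.905 are unchanged.

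If the sponsor intends whole-bladder response instead, state that a new lesion is failure and takes precedence over every row, say how a new lesion without histology is scored, and restate power on that definition. If P1 = 0.30 is a marker-response rate, power falls to about 0.85-0.89 at the assumed rates of 3.7-10.4%, and lower if new tumours are more frequent.

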**Eligibility criteria:**

**Inclusion**

1. Males and females age 21 or older.
2. Histologic evidence of urothelial carcinoma of the bladder.
3. Low/Intermediate-risk papillary urothelial carcinoma of the bladder, at initial occurrence or recurrent with >6 months interval free of disease.
4. Patients with multifocal tumors must have resectable lesions.
5. Patients may be treatment-naïve or have failed previous regimen of intravesical therapy.
6. At least one endoscopically measurable tumor 6 - 10mm in diameter.
7. Adequate hepatic and renal function normal ranges defined as:  
Creatinine 0.6-1.3 MG/DL  
BUN 10-20 MG/dL  
AST (SGOT) 5-35 U/L  
ALT (SGPT) 7-56U/L  
GGT 0-45U/L
8. Patient or authorized proxy needs to have signed the informed consent form.

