### Office visit on 2nd Resection only occurs if patient had a single Tumor during 1st Resection. All patients with Multiple tumors at 1st Resection will have 2nd Resection in an outpatient hospital setting.

#### Completed per PI description

## **Procedures:**

**Aim 1 Procedures:** Transurethral resection of bladder tumors is a well-defined surgical technique used for diagnosis, staging, and treatment of bladder tumors of different stages. Briefly, patients undergo general anesthesia. Under proper aseptic technique, an optical resectoscope with video imaging capabilities is introduced into the bladder retrogradely via the urethra. The bladder tumor is resected using a resection loop connected to an electric source. The technique involves scooping movements of the loop, while cauterization is applied, to allow concomitant tissue cut and hemostasis. Measurement of the lesions will be performed by comparison with the standardized size of the resection loop.

Collection of samples: Biopsies of the marker lesion and normal appearing mucosa located remotely from the marker lesion will be processed using standard procedures for formalin fixation and paraffin embedding. These tissues will be tested by immunohistochemistry for Ki-67 and TUNEL. Each specimen will also be stained with hematoxylin and eosin to verify urothelial carcinoma histology.

**Aim 2 Procedures:** Collection of samples: Biopsies of the marker lesion and normal mucosa remote from the marker lesion will be processed using standard procedures for formalin fixation and paraffin embedding. The pretreatment biopsy of the marker lesion will be performed with a 2mm cold-cup biopsy forceps, to avoid affecting the histologic characteristics of the marker lesion. Because of the limited amount of tissue yield in this biopsy, we will only perform immunohistochemistry analyzing Ki-67, TUNEL, ER $\alpha$  and ER $\beta$ -1. The normal bladder biopsies, the resection of additional tumors synchronous to the marker lesion (in case of multiple lesions), and the final definitive resection of the marker lesion will be performed with a regular rigid biopsy forceps or resection loop, yielding much larger specimen fragments. These tissues will be tested by immunohistochemistry and RT-qPCR for the mRNA of ER $\alpha$ , ER $\beta$ -1, ER $\beta$ -2 and ER $\beta$ -5. Each specimen will also be stained with hematoxylin and eosin to verify urothelial carcinoma histology.

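### A negative final biopsy counts as success, but no rule says what follows if the marker lesion's own baseline biopsy shows no carcinoma

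*Combined protocol and SAP*

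**What the plan says.** **Endpoint.** Under End-points/Statistical considerations, a patient is a success if cystoscopy shows CR or PR, or if "the biopsy of a residual tumor or the bed of the lesion (in case of a CR) is negative for bladder cancer". The summary table follows this. A negative final biopsy gives an overall CR after cystoscopic CR, PR, SD and even PD. The combined PR/SD row adds a remark about absence of viable tumour alongside necrotic, fibrotic or scarred tissue. Neither the prose rule nor the PD row carries that remark.

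**Eligibility.** Inclusion item 2 asks for "Histologic evidence of urothelial carcinoma of the bladder", a condition on the patient. Item 3 asks for low/intermediate-risk papillary carcinoma, at first occurrence or recurrent after more than six months free of disease. Item 6 asks for one tumour of 6 to 10 mm, measurable endoscopically. None of the three refers to the histology of the marker lesion.

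**Evaluability.** Under Sample Size, an evaluable patient meets all eligibility criteria and has had at least 30 days of tamoxifen.

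**Baseline biopsy.** The Overall study description has a 2 mm cold-cup biopsy of the marker lesion in every patient, "to rule out a potential high-grade lesion" and for pretreatment immunohistochemistry. The Procedures section adds: "Each specimen will also be stained with hematoxylin and eosin to verify urothelial carcinoma histology". It does not say what follows if carcinoma is not found.

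**The concern.** A biopsy-based response means that carcinoma was there before treatment and is absent after it. The plan makes only the second half a condition of success.

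A patient with several tumours can meet the histology criteria from the lesions that are resected, while the one left in place is benign. A recurrent patient might meet item 2 from an earlier tumour. In either case the patient stays evaluable under the stated rule. A final biopsy without cancer can then be entered as a CR, although there was no cancer in that lesion to respond.

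The trial has no control group and a low bar for success, so a few such patients could change the primary conclusion.

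**Working it through.** **Inputs, all from Sample Size**
- Response rates: "the bad response rate (P0) is 0.05, the good response rate (P1) is 0.30".
- Error rates: alpha 0.05, and in the same sentence "power is 0.90, and confidence interval is 95" percent.
- Size: "the maximum sample size is 17 and the minimum sample size is 9".
- Stage 1: "The first stage of the study will include 9 patients. If there are 0 responses observed, the trial will be stopped accepting H0".
- Final rule: reject H0 with 3 or more successes in 17.
- Drop-out 10%, 19 enrolled.
- Share q of marker lesions that never held carcinoma: **not in the documents, assumed**.

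**Step 1: reproduce the plan.** Let X1 ~ Bin(9, p) be the stage-1 successes and X2 ~ Bin(8, p) the stage-2 successes. Then

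P(reject) = P(X1=1)·P(X2≥2) + P(X1=2)·P(X2≥1) + P(X1≥3).

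At p = 0.05:
- P(X1=0) = 0.95^9 = 0.6302
- P(X1=1) = 9 × 0.05 × 0.95^8 = 0.2985
- P(X1=2) = 36 × 0.05² × 0.95^7 = 0.0629
- P(X1≥3) = 0.0084
- P(X2≥2) = 0.0572 and P(X2≥1) = 0.3366

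P(reject) = 0.2985 × 0.0572 + 0.0629 × 0.3366 + 0.0084 = 0.0171 + 0.0212 + 0.0084 = 0.0466, after rounding.

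At p = 0.30 the same formula gives a power of 0.9045. A search over designs up to n = 35 confirms that 0/9 and 2/17 give the optimal design. For enrolment, 17/0.9 = 18.9, rounded up to 19. The stated design is reproduced.

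**Step 2: sensitivity to q.** Assume that every never-malignant marker lesion is scored a success, and that the 5% null rate applies to the rest. The null success rate becomes

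p = 0.05(1 − q) + q = 0.05 + 0.95q.

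| q (assumed) | null success rate | type I error |
|---|---|---|
| 0 | 0.0500 | 0.047 |
| 1% | 0.0595 | 0.071 |
| 2% | 0.0690 | 0.101 |
| 3% | 0.0785 | 0.135 |
| 5% | 0.0975 | 0.212 |
| 10% | 0.1450 | 0.433 |

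Type I error passes 0.05 at q of about 0.15%, because the design starts at 0.0466.

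**Step 3: the same by count.** Suppose exactly one of the 17 lesions is such a case, in random position, and the drug has no effect.
- In stage 1 (weight 9/17), rejection needs two or more successes among the other 16: 1 − 0.95^16 − 16 × 0.05 × 0.95^15 = 0.1892.
- In stage 2 (weight 8/17), rejection needs either one success in the first 9 and at least one in the other 7, or two or more in the first 9: 0.2985 × 0.3017 + 0.0712 = 0.1613.

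The weighted sum is 9/17 × 0.1892 + 8/17 × 0.1613 = 0.176.

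**Step 4: enrolment under the fix.** If a share f of patients has an unconfirmed baseline marker biopsy and is replaced, enrolment is 17/(0.9(1 − f)):
- f = 5%: 17/0.855 = 19.9, so 20
- f = 10%: 17/0.81 = 20.99, so 21
- f = 20%: 17/0.72 = 23.6, so 24

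**The case against.** The plan clearly intends the marker lesion to be carcinoma. It must be papillary, it is always biopsied, and every specimen is stained to check for carcinoma. The sample-size section calls it a bladder cancer lesion. Four further points narrow the gap.

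- **Solitary tumours.** At first occurrence, the marker biopsy is the only apparent source of the required histology. A benign result fails inclusion items 2 and 3, so the patient is not evaluable. Item 3 reads most naturally as describing the current episode, which would protect a solitary recurrence too. This stands. The clear remaining case is the multifocal patient.
- **The PR/SD row.** Its remark on necrosis, fibrosis or scar can be read as asking for a visible treatment effect, which an unchanged benign lesion might not show. This stands in part. The prose rule and the PD row lack the remark. The Marker lesion study design section also says that a pilot study is still being completed to show that the baseline biopsy does not itself cause such changes.
- **Non-diagnostic samples.** A reader might infer that any patient without confirmed baseline carcinoma is a near-certain success. The documents do not support that. A 2 mm sample can miss a real tumour, and the larger week-12 resection may then show it. With SD or PD that patient is a failure.
- **Size.** A reader might also infer that the true null success rate exceeds 5%. That would need a value of q, which the documents do not give. They also do not say whether the planned 5% already allows for such lesions.

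What survives is that the staining sentence describes a check without a consequence. It also covers normal-mucosa specimens, so it cannot serve as an evaluability rule.

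**Conclusion.** The gap is real but limited. The plan as written can count a marker lesion that never held carcinoma as a response, because success by negative final biopsy is not tied to carcinoma in that lesion's own baseline biopsy. The exposure lies mainly in multifocal patients and possibly in recurrent ones.

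The sample-size calculation is correct for its stated inputs. The type I error figures rest on two assumptions: a value of q, and that every such lesion is scored a success. They show that a design needing 3 of 17 has little tolerance for misclassified successes. They do not show that this trial's type I error is inflated.

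**What to change.** 1. In Sample Size, add to the definition of an evaluable patient, for the primary endpoint, that the baseline biopsy of the marker lesion itself shows urothelial carcinoma on H&E. State that this is decided from the baseline report, before the week-12 result is known. Apply it to the 9 patients of stage 1 as well as to the full 17.
2. In End-points/Statistical considerations, state in the prose rule and in the table that a negative final biopsy counts toward success only in such patients.

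With 17 evaluable patients so defined, the planned alpha of 0.0466 and power of 0.905 are unchanged. The biopsy and stain are already planned for everyone.

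The cost is that patients with benign or non-diagnostic baseline tissue become non-evaluable for efficacy and need replacing. Some of them will have true cancers with inadequate samples. Enrolment would be about 20 at 5% unconfirmed and 21 at 10%, against 19 planned, at a centre that sees 10 to 12 such cases a year. These patients remain in the safety set. The change concerns analysis only and does not bear on how they are treated.
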